6.5.3 Vital Signs

Vital signs (systolic blood pressure, diastolic blood pressure, and pulse rate) will be summarized using mean, standard deviation, minimum, maximum and median by treatment group and visit. Additionally, a within-subject change will be calculated per visit as the post-baseline measurement minus the baseline measurement and summarized by treatment group and visit.

6.5.4 Electrocardiograms

ECG variables will be summarized using mean, standard deviation, minimum, maximum and median for each treatment group at each treatment visit and time point, including changes from baseline.

Number and percent of subjects with normal and abnormal results as assessed by the central reader for the 12 lead ECG will be tabulated by treatment group at each treatment visit and time point.

| | QTc Interval Criteria Value (msec) | |
|------------------------|------------------------------------|--|
| Normal | \leq 450 | |
| Borderline | > 450 | |
| Prolonged | > 480 | |
| Clinically significant | > 500 | |

The QTc interval will be summarized using frequency tables for each treatment visit and time point for values of clinical importance using the range criteria below.

Number and percent of subjects with 12 lead ECG abnormalities as well as number and percent of subjects whose 12 lead ECG reading changed from normal at baseline to abnormal will be tabulated by treatment group at each treatment visit.

6.5.5 Other Safety-Related Assessments

C-SSRS results will be summarized by treatment group and visit.

6.6 Analysis of Pharmacokinetics

The statistical methods for PK data will be described in a separate analysis plan. Results of the population PK analysis will not be reported in the Clinical Study Report but in a separate population PK report.

Plasma concentration of fezolinetant and ES259564 will be listed.

6.6.1 Estimation of Pharmacokinetic Parameters

All details of the population PK analysis will be described in a separate analysis plan.

6.7 Analysis of Pharmacodynamics

Serum concentrations of sex hormones (LH, FSH, E2, Testosterone Total/Free, Androstenedione, DHEA, Estrone) and SHBG will be summarized using descriptive statistics (number of subjects, mean, SD, median, minimum and maximum) for each visit and time point and for change from the baseline to each postdose visit, if the data is available

6.8 Other Analyses

Not applicable.

6.9 Interim Analysis (and Early Discontinuation of the Clinical Study)

There will be no interim analysis.

6.10 Additional Conventions

6.10.1 Analysis Windows

Study Day for analysis windows during the double-blind treatment phase will be calculated as date of visit/assessment – first dose date +1.

Study Day for the follow-up phase will be calculated as date of visit/assessment – last dose date of double-blind treatment.

As noted in Section 1 only data pertaining to the double-blind treatment phase will be used in the 12-week treatment phase analysis:

- The active treatment extension period data (beginning from the second day of the active treatment extension period) will be excluded, assuming the Week 12 assessments are done before the first dose of active treatment extension period.
- Follow-up data that also falls into the active treatment extension period will be excluded (i.e., early discontinuations within the active treatment extension period phase).

6.10.1.1 Efficacy Analysis Windows

For the analysis windows (weeks prior to the extension period), the last day is always the last day of exposure to double-blind treatment. For VMS diary data the last day of exposure includes events reported until 8:00AM the following day. For example, the Week 1 average will include diary data from 8AM on Day 1 through 7:59AM on Day 8.

For both VMS and non-VMS efficacy, the end of overall treatment is defined as the last day of treatment (e.g., discontinued study or entered follow-up period) and the follow-up period begins at last overall treatment + 1 day.

| Analysis study week | Analysis window |
|-------------------------|--|
| Baseline | Non-missing days from D-10 up to and including D-1 |
| Week 1 | D1 to D7 |
| Week 2 | D8 to D14 |
| Week 3 | D15 to D21 |
| Week 4 | D22 to D28 |
| Week 5 | D29 to D35 |
| Week 6 | D36 to D42 |
| Week 7 | D43 to D49 |
| Week 8 | D50 to D56 |
| Week 9 | D57 to D63 |
| Week 10 | D64 to D70 |
| Week 11 | D71 to D77 |
| Week 12 | D78 to D84 |
| Extension period visits | Defined in extension period SAP |

The study week determination for the vasomotor symptoms data is based on the following:

A weekly average will be calculated if any information, including zero VMS events, for 4 or more days was reported.

All other efficacy assessments, including those from unscheduled visits and regardless of visit label, will be allocated to analysis visits based on the table below:

| Target day | Analysis window | Analysis visit |
|---------------------|---|-------------------------|
| D1 | last non-missing value on or prior to day 1 | Baseline |
| D29 | D22 to D36 | Week 4 |
| D85 | D72 to Day 92 | Week 12 |
| Beginning on Day 99 | Defined in extension period SAP | Extension period visits |

If more than one observation exists within the analysis window, the observation closest to the scheduled visit day will be selected for that visit. If there are two observations that have the same distance from the scheduled day, the value that is before the scheduled day will be selected in the analysis. If more than one observation is made on the same day, an average value if continuous, or the worst value if categorical, will be included in the analysis.

6.10.1.2 Safety Analysis Windows

Except for adverse events, for the analysis window (weeks prior to the follow-up period), data within 1 day after the last day of exposure to double-blind treatment will be included.

The end of overall treatment is defined as the last day of treatment (e.g., discontinued study or entered follow-up period) +1 and the follow-up period begins at last overall treatment + 2 days and onward.

The data summary by visits will be done following the analysis windows specified in the table below:

| Analysis | Scheduled Day in Protocol | Analysis Windows (day) | | |
|----------------------------|---|---|----------|----------|
| Visits | | a) | b) | c) |
| Baseline | Day 1 | Last non-missing value on or priot to day 1 (inclusive) | | |
| Week 2 | Day 15 | 2 to 22 | | |
| Week 4 | Day 29 | 23 to 43 | 2 to 43 | 2 to 57 |
| Week 8 | Day 57 | 44 to 71 | 44 to 71 | |
| Week 12* | Day 85 | 72 to 92 | 72 to 92 | 58 to 92 |
| Extension Period Visits | Beginning on day of first dose of extension period treatment | Defined in extension period SAP | | |

a) Apply to liver biochemistry and INR testing

- b) Apply to complete Clinical laboratory and urinalysis, Vital signs
- c) Apply to Blood PD/PK sample

*The analysis window for the Week 12 ECG assessment (Target Day 85) is Day 2 through Day 92

If more than one observation exists within the analysis window, the same rules will be followed as described above for efficacy analysis visit windows, except that if there are two observations that have the same distance from the scheduled day, the value that is after the scheduled day will be selected in the analysis.

6.10.2 Imputation Rules for Incomplete Dates

In case of missing partial start and stop dates for concomitant medications or targeted medical history, the following rules will be used:

If the start date is missing or partial:

- if the month is missing, use January
- if the day is missing, use the first day of the month under consideration
- if the year is missing, use year of the informed consent date
- if the entire date is missing, use informed consent date

If the stop date is missing or partial:

- if the month is missing, use December
- if the day is missing, use the last day of the month under consideration
- if the year or the entire date is missing, set the stop date to December 31st, 2099

If the imputed start date is after the stop date, then the imputed start date will be 1 day prior to the stop date.

For AEs, a missing or incomplete onset date will be imputed according to the following conventions.

If an onset date is missing, the imputed onset date will be the date of first dose of study drug.

If only the year is known for the AE onset date, the imputed onset date will be the latest of the following non-missing dates:

- Date of first dose of study drug
- January 1 of the year of AE onset date

If only the month and year is known for the onset date, set the surrogate onset date to the first day of that month and then apply the following rules.

- If the month and year of the onset date is prior to the month and year of the first dose of study drug, then the surrogate onset date will be the imputed onset date.
- If the month and year of the onset date is on or after the month and year of the first dose of study drug, then the imputed onset date will be the latest of the following non-missing dates:
 - Date of first dose of study drug
 - Surrogate onset date

If the imputed onset date is after the adverse event end date, the imputed onset date will be the same as the adverse event end date.

7 **REVISION AND RATIONALE**

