7.9 Additional Conventions

Missing data may be the result of missing week 4/week 12 frequency/severity of VMS measurements or the result of patients discontinuing treatment prior to week 4/week 12. Missing at random will be assumed. Details will be provided in the SAP.

The start and stop dates of AEs and concomitant medication will be imputed. The imputed dates will be used to allocate the concomitant medication and AEs to a treatment group, in addition to determining whether an AE is/is not treatment emergent. Listings of the AEs and concomitant medications will present the actual partial dates; imputed dates will not be shown. See the SAP for details of the definition for analysis windows to be used for analyses by visit.

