6.5.1 Adverse Events

Per protocol, a TEAE is defined as an AE observed after starting administration of the study drug and up to 21 days after the last dose of the study drug.

A TEAE during the DB period, is defined as an AE observed after starting administration of the study drug and up to 21 days after the last dose of the double-blind study drug, and before the first dose of treatment for extension phase for subjects who entered extension treatment period.

A study drug-related TEAE is defined as any TEAE with a causal relationship of YES by the investigator.

The sponsor has a list of events that they classify as "always serious" events. If an AE is reported that is considered by the sponsor to be an SAE per this classification as "always serious", the AE will be treated as an SAE in tables and listings, and flagged as 'always serious' in AE listings.

An overview table will include the following

- Number of TEAEs,
- Number and percentage of subjects with TEAEs,
- Number of drug related TEAEs,
- Number and percentage of subjects with drug related TEAEs,
- Number of serious TEAEs,
- Number and percentage of subjects with serious TEAEs,
- Number of serious drug related TEAEs,
- Number and percentage of subjects with serious drug related TEAEs,
- Number of TEAEs leading to permanent discontinuation of study drug,
- Number and percentage of subjects with TEAEs leading to permanent discontinuation of study drug, and
- Number of deaths.

The number and percentage of subjects with TEAEs in the following AE categories will be summarized by system organ class (SOC), high level term (HLT) and preferred term (PT):

- TEAEs,
- Drug-related TEAEs.

The number and percentage of subjects with TEAEs in the following AE categories will be summarized by SOC and PT:

- Serious TEAEs,
- Drug-related serious TEAEs,
- TEAEs leading to permanent discontinuation of study drug,
- Drug-related TEAEs leading to permanent discontinuation of study drug,
- TEAEs that equal to or exceed a threshold of 5% in any treatment group (threshold is based on PT),
- TEAEs excluding serious adverse events that equal to or exceed a threshold of 5.0% in any treatment group.

The number and percentage of subjects with TEAEs, as classified by PT only, will be summarized for each treatment group.

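### An AE whose only recorded onset date is the calendar year before first dose is imputed to Day 1 and becomes treatment-emergent, unless it ended before dosing

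*SAP*

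**What the plan says.** Section 6.10.2 of the 12-week SAP handles an incomplete AE onset date according to how much of it is known.

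- **Nothing known:** the onset becomes the "date of first dose of study drug".
- **Year only:** "If only the year is known for the AE onset date, the imputed onset date will be the latest of the following non-missing dates". The two candidates are first dose of study drug and "January 1 of the year of AE onset date". No separate provision is made for an onset year before the dosing year.
- **Month and year:** the first day of the month is a surrogate date. If that month precedes the first-dose month, "then the surrogate onset date will be the imputed onset date". Otherwise the later of first dose and the surrogate is used.
- **End-date cap:** an imputed onset that falls later than the day the event ended is moved back to that day.

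Protocol 7.9 gives imputed dates two uses: allocating events to a treatment group, "in addition to determining whether an AE is/is not treatment emergent". It adds that listings will show the partial dates as recorded.

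The 12-week SAP, Section 6.5.1, defines the relevant category: "A TEAE during the DB period, is defined as an AE observed after starting administration of the study drug". Section 6.10.2 of the 52-week SAP repeats the imputation wording, but Section 6.5.1 of that SAP counts TEAEs from the start of fezolinetant.

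**The concern.** An onset year earlier than the dosing year proves that the event began before treatment. The month-and-year rule uses that kind of information; the year-only rule discards it. Two records of the same event in the same subject, one giving December 2019 and one giving 2019, can then fall on opposite sides of first dose. The vaguer record is the one that becomes treatment-emergent, although both establish a pre-dose start.

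At stake is the TEAE tabulation. A pre-treatment event would be counted as arising on study drug, while the listing for the same subject showed an onset year before she was dosed.

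**Working it through.** The plan gives no figure to reproduce. The check is to apply the rules literally to test dates.

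**Inputs.** The imputation rules and end-date cap come from 12-week SAP 6.10.2. AE collection starts at consent (Protocol 5.5.1). Screening lasts up to 35 days (Protocol 2.2.1), or 50 days when a biopsy must be repeated (Protocol 5.4.7). The planned study period starts in Q3 2019 (Protocol synopsis), and all planned subjects were randomized before recruitment was paused on 30 March 2020 (Appendix 1 of both SAPs). The first-dose date of 20 January 2020 used below is illustrative.

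**General result.** Let F be the first-dose date and Y the onset year. The year-only rule gives max(F, 1 January Y). If Y is earlier than the year of F, 1 January Y precedes F, so the result is always F.

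**Test cases, F = 20 January 2020**

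| Recorded onset | AE end | Calculation | Imputed onset | Position |
|---|---|---|---|---|
| 2019 | ongoing | max(20 Jan 2020, 1 Jan 2019) | 20 Jan 2020 | Day 1 |
| 2019 | 5 Feb 2020 | same maximum; cap not triggered | 20 Jan 2020 | Day 1 |
| 2019 | 10 Jan 2020 | same maximum, then capped | 10 Jan 2020 | pre-dose |
| Dec 2019 | ongoing | surrogate date stands | 1 Dec 2019 | pre-dose |
| 2020 | ongoing | max(20 Jan 2020, 1 Jan 2020) | 20 Jan 2020 | Day 1 |
| Jan 2020 | ongoing | max(20 Jan 2020, 1 Jan 2020) | 20 Jan 2020 | Day 1 |

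Rows 1 and 2 are wrong, because the recorded year rules out the imputed date. Row 4 shows the section classifying the more precise record correctly. Row 3 shows that the cap rescues only events that ended before first dose. Rows 5 and 6 are the intended conservative default, since the order of onset and dosing is unknown there.

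**When the case can arise.** The AE must start between consent and 31 December 2019, with first dose in 2020. The latest possible first dose is:

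- 35-day screening: 31 December 2019 + 35 days = 4 February 2020.
- 50-day screening: 31 December 2019 + 50 days = 19 February 2020.

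**52-week SAP.** For subjects originally randomized to fezolinetant, first dose of study drug and first dose of fezolinetant are the same date, so rows 1 and 2 apply unchanged. For placebo-to-fezolinetant subjects, first dose of study drug, read literally, is placebo Day 1. With F = 20 January 2020 and 84 days of placebo, fezolinetant would start on 13 April 2020. An onset imputed to 20 January precedes that date and is not treatment-emergent in the 52-week analysis. The baseline table in Section 5 of that SAP agrees: it sets the TEAE baseline for these subjects at Week 12.

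**The case against.** The strongest defence is that dating an uncertain onset to first dose is a standard conservative choice: it errs toward counting an event as treatment-emergent and hides no safety signal. That holds when the order of onset and dosing is unknown. It does not hold when the recorded year settles the order, and the month-and-year rule shows that the plan accepts this.

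The second defence is rarity, and it largely stands. Conditions before consent are medical history (Protocol 5.2.2), so an affected AE would start within a few weeks of dosing. Sites enter data within 5 days of a visit, and monitors check entries against source (Protocol 8.1). A month would usually be obtainable, and the month-and-year rule would then classify the event correctly.

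Four stronger readings might be inferred, and the documents do not support them.

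- **The rule favours an arm.** The 12-week rule is identical for all three arms and does not touch efficacy.
- **All four groups in the 52-week analysis are affected.** As worded, the two placebo-to-fezolinetant groups are not.
- **Screening is known to have crossed the year end.** The Q3 2019 date is a planned study start, and no actual first or last randomization date is given. The overlap is plausible but assumed.
- **The recorded year is lost.** Listings keep the partial date; only the tabulated classification changes.

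**Conclusion.** The year-only rule is wrong as written for one narrow class of event: an onset year before the year of first dose, with the event not over before first dose. This applies in the 12-week analysis for all arms and in the 52-week analysis for subjects originally randomized to fezolinetant.

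The importance is low. The number of affected events cannot be computed because the documents give no count of year-only onsets; few or none are expected. Any effect would be a slight inflation of TEAE counts.

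The conclusion rests on two assumptions. One is that screening spanned the 2019/2020 year end for some subjects. The other is that an onset dated Day 1 without a time counts as treatment-emergent. The TEAE definition does not say so, but imputing to the first-dose date has little purpose otherwise. For that reason misclassification of every such event should not be called certain.

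**What to change.** Add a condition to the year-only rule in Section 6.10.2 of both SAPs, mirroring the month-and-year rule:

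> If the onset year is before the year of first dose of study drug, the imputed onset date is January 1 of the onset year (not treatment-emergent); otherwise use the latest of the two dates.

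With first dose on 20 January 2020, the year-only 2019 records in rows 1 to 3 of the table all move to 1 January 2019, which is pre-dose. The year-only 2020 record stays at 20 January 2020. The imputed 1 January may precede consent, but imputed dates are not listed and only the order relative to first dose matters for TEAE status.

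In the 52-week SAP, the same edit is a chance to state which first dose anchors imputation for placebo-to-fezolinetant subjects, since the imputation rule refers to study drug and the TEAE definition to fezolinetant.

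The cost is one sentence in each SAP and one program condition. If the SAPs are already final, the change can be documented and justified in the clinical study report, as Section 1 of each SAP provides.

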7.1 List of Changes in SAP Version 2.0

The changes from the Version 1 to Version 2 that may impact the statistical analyses are listed in the table below:

| SAP Sections | Description | Rationale | | |
|----------------------|--|--|--|--|
| Relevant sections | Added additional statistical analysis due to COVID-19 | To evaluate potential impact of COVID-19 | | |
| 5.2.2 | Moved PGI-C to Secondary endpoints Section | To be consistent with the protocol amendments (version 3.0) | | |
| 5.3 | Added 75%, 90% responder endpoints | To add clinically relevant exploratory endpoints | | |
| 5.3, 5.3.1 | Added an endpoint in the severity of moderate and severe VMS (include only moderate and severe VMS events in the calculation) | To extend the endpoints in a sensitivity analysis to exploratory endpoints for all visits | | |
| 5.3, 5.3.1, 6.4.4 | Added an endpoint in daily frequency of moderate and severe VMS for the first week | To explore early onset by adding daily VMS frequency for the first week | | |
| 5.3.1, 6.4.4 | Removed Frequency and severity of 12- hour daytime and nighttime VMS events. | Planned not to perform analysis on the 12-hour daytime and nighttime VMS events | | |
| 6.2.3, 6.2.4 | Removed analysis on FAS from demographics and baseline characteristics, medical history/medication Sections | The planned analysis on SAF is sufficient to provide information | | |
| 6.4.1.3 | Added subgroup on Age (<55, >=55) | To add medically meaningful subgroups | | |
| 6.4.1.4 | Added conditional analysis based on clinical meaningfulness of the statistical change in moderate to severe hot flash frequency | Potentially in supporting the primary endpoints | | |
| 6.5.1 | Modified the list of AESIs | To be consistent with the protocol amendments (version 3.0) | | |
| 6.5.2.1 | Added a category for liver assessment, (ALT or AST > 3xULN) and ALP< 2xULN and Total Bilirubin > 1.5xULN | To be aligned with CIOMS Guidance 2020 | | |
| 6.5.4 | Removed the summary of QTc change from baseline outliers | The summary of QTc change from baseline outliers provides limited additional medical relevant information | | |

7.2 List of Changes in SAP Version 3.0

The changes from the Version 2 to Version 3 that may impact the statistical analyses are listed in the table below:

| SAP Sections | Description | Rationale |
|----------------|--|---|
| 6.4.1.4, 6.4.4 | Removed Section 6.4.1.4 on conditional analysis based on clinical meaningfulness of the statistical change in moderate to severe hot flash frequency, and added the analysis to Section 6.4.4 (Analysis of Exploratory Endpoints) | To reflect FDA's feedback. |
| 6.5.2.1 | Removed the category for liver assessment, (ALT or AST > 3xULN) and ALP< 2xULN and Total Bilirubin > 1.5xULN | The analysis of this category is only planned for Integrated Summary of Safety. |

8 **REFERENCES**

- James R. Carpenter, James H. Roger & Michael G. Kenward (2013) Analysis of Longitudinal Trials with Protocol Deviation: A Framework for Relevant, Accessible Assumptions, and Inference via Multiple Imputation, Journal of Biopharmaceutical Statistics, 23:6, 1352-1371, DOI: 10.1080/10543406.2013.834911
- EMA CHMP Guideline On Clinical Investigation Of Medicinal Products For Hormone Replacement Therapy Of Oestrogen Deficiency Symptoms In Postmenopausal Women [EMEA/CHMP/021/97 Rev. 1]. October 2005. Available at: https://www.ema.europa.eu/en/clinical-investigation-medicinal-products-hormonereplacement-therapy-oestrogen-deficiency-symptoms.
- EMA/CHMP (2020a), Guidance to Sponsors on How to Manage Clinical Trials During the COVID-19 Pandemic, https://www.ema.europa.eu/en/documents/press-release/guidancesponsors-howmanage-clinical-trials-during-covid-19-pandemic_en.pdf
- EMA/CHMP (2020b), Points to Consider on Implications of Coronavirus Disease (COVID-19) on Methodological Aspects of Ongoing Clinical Trials, EMA/158330/2020. Available at: https://www.ema.europa.eu/en/documents/scientific-guideline/points-considerimplicationscoronavirus-disease-covid-19-methodological-aspects-ongoing-clinical en.pdf
- EuroQol Research Foundation. EQ-5D-5L: About. Version 18 Apr 2017. Available at https://euroqol.org/eq-5d-instruments/eq-5d-5l-about/. Accessed 11 Oct 2018.
